C 12.1 Individual Participant Pause and Stopping Criteria.....	35
C 12.2 Study and/or PSA Pause and Stopping Criteria	36
C 13 STATISTICAL CONSIDERATIONS.....	37
C13.1 Statistical Hypotheses	37
C 13.4 Primary Endpoint/Estimand Analysis	37
C 13.5 Outcome Measures and Statistical Analyses	38
C 13.5.1 Early Treatment	38
C 13.6 Interim Analysis Plan	41
C 13.7 Final Analysis Plan.....	42
C 13.9 Sample Size Determination	42
APPENDIX C ABBREVIATIONS	44
APPENDIX C AMENDMENT HISTORY.....	45
APPENDIX C REFERENCES.....	48
C Supplement 1. CYP3A4 Strong Inhibitors and Sensitive Substrates	49

List of Tables

Table 1 Product Specific Criteria for Study Pause	36
Table 2 Analysis Schedule and Actions Reviewed at Interim Analysis.....	41
Table 3 Operating Characteristics for the Adaptive Design Including Superiority and Futility for a Range of Assumed Event (Symptomatic COVID-19) Rates for Upamostat Active Treatment and Upamostat Control Arm	43

C 1 PROTOCOL SUMMARY

C 1.1 Study Synopsis

PSA Title:	A Phase 2 safety and efficacy study of upamostat for early outpatient treatment of COVID-19
Overall Study Description:	This study is a global, multicenter, adaptive, randomized, double blind, platform trial evaluating promising investigational products (IP) for early outpatient treatment of SARS-CoV-2 infection
Objectives:	
Primary:
 
To determine if early treatment with upamostat can shorten time to sustained symptom alleviation or resolution in participants infected with SARS-CoV-2.
 
Secondary:
 
 • To determine if early treatment with upamostat can reduce disease severity in participants infected with SARS-CoV-2 • To determine if early treatment with upamostat can decrease the incidence of hospitalization due to COVID-19 • To evaluate virologic efficacy of upamostat compared to placebo • To evaluate the safety and tolerability of upamostat compared to placebo 
Exploratory:
 
 • To determine the presence and titer of antibodies to SARS-CoV-2 at baseline, the development of antibodies during study participation, and their association with clinical outcome • To assess the impact of host transmembrane protease polymorphisms on drug efficacy

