- n. **PK sampling will be performed. All participants will have Day 0 sampling prior to administration of study drug and Day 14 sampling approximately 22-26 hours after the last dose of study medication. Participants will then follow one of two schedules for Day 3 sampling (see [Section 9.2.6 Pharmacokinetic Testing](#)). Study staff may call participant the day prior to the Day 3 sampling to remind them of timing of upamostat dose and venous blood sampling.**
- o. **A sample of whole blood will be stored for planned future host protease polymorphism assessment**

C 3 INTRODUCTION

C 3.1 Study Rationale

There are four main sub-groupings of coronaviruses (classes alpha, beta, gamma, and delta). SARS-CoV-2 is a member of the beta class coronaviruses that also include the close relatives SARS-CoV (the first identified severe acute respiratory syndrome-related coronavirus) and MERS-CoV (Middle East respiratory syndrome-related coronavirus). All three viruses predominantly attack the respiratory system, but can also impact the gastro-intestinal system, heart, kidney, liver, and central nervous system, potentially leading to the failure of multiple organs.

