The unique number will be the only participant identifier used on all sample collections and return of results. The site's blinded pharmacist or qualified designee will provide each participant with study drug and instructions for use; the initial doses for Day 0 will be given at the site.

C 7.2.5 Product Storage and Stability

Investigational drug must be kept in an appropriate, limited-access, secure place at controlled room temperature 15° to 25°C (60° to 77°F) and protected from light until it is used or returned to the industry supporter or designee for destruction. Investigational drug must be stored under the conditions specified on the label and remain in the original container until dispensed. A daily temperature log of the drug storage area must be maintained every working day while the drug is still in the research unit.

C 7.2.6 Preparation

All bottles provided contain 30 capsules of 200 mg upamostat or placebo and are prelabelled according to country specific requirements. 1 bottle will be dispensed to each participant at Day 0.

C 7.4 Measures to Minimize Bias: Randomization and Blinding

C 7.4.1 Randomization

Once randomized to the upamostat early treatment indication, participants will undergo a second, blinded randomization to either upamostat or placebo through the Interactive Voice/Web Response System (IxRS). Probability of randomization will be dependent on the number of products enrolling in the early treatment indication at that time.

The ratio of assignment to upamostat or placebo will be r:1 where r is the number of IPs concurrently enrolling in the early treatment indication that a given participant is eligible to receive. For example, if two products are enrolling in the treatment indication simultaneously, the probability of randomization of an eligible participant to upamostat or placebo will be 2:1. See also [Section C 13 Statistical Considerations](#).

The site research pharmacist(s) will be responsible for maintaining secure access to randomization assignments through the IxRS.

C 7.4.2 Blinding and Unblinding

Both participants and study investigators will be blinded to this second randomization.

Refer to the Master Protocol regarding unblinding.

C 7.6 Concomitant Therapy

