- Screening Symptom Questionnaire (repeat if visit not performed on same day as Screening)
- Randomization (Step 1)
- Study (IP) Informed Consent (in person)
- Screening assessments (see [Section C 9.2.3 Screening Assessments](#))
- **ECG**
- Eligibility evaluation (review of all screening and eligibility assessments)
- Randomization (Step 2)
- Upper respiratory specimen collection (prior to administration of upamostat or control) (for efficacy assessment)
- Venous blood sampling (prior to administration of upamostat or control)
 - Hematology (prior to administration of upamostat or control)
 - Chemistry (prior to administration of upamostat or control)
 - **Coagulation Studies**
 - **Anti-SARS-CoV-2 IgM and IgG**
 - **Polymorphisms of relevant host cellular proteases**
 - **Whole Blood, Plasma and Serum Storage for Possible Future Research (prior to administration of upamostat or control)**
 - **Pharmacokinetics**
- **Administration of upamostat or control**
- Collect and update contacts
- Dispense study kit
- Adverse event recording and reporting

C9.4.3 Day 3 Visit – ~~Remote~~ or In Person

This visit is scheduled to take place In Person on Day 3. Every effort should be made to complete the Day 3 visit requirements on Day 3; however, the visit may take place — if necessary +/- 1 days.

- ~~SARS-CoV-2 Vaccination Status~~
- Concomitant medication review
- Collect and update contacts
- Daily Symptom Follow Up Questionnaire (daily until day 28 then at **Weeks 8** and 12)
- Upper respiratory specimen collection
- Clinical outcome assessment
- Vital signs
- Physical exam
- Venous blood sampling (for Pharmacokinetics Group A: venous blood sampling should be collected within 2 hours prior to administration of upamostat or control, for Pharmacokinetics Group B: venous blood sampling should be collected 2-4 hours after administration of upamostat or control)
 - Hematology
 - Chemistry
 - **Coagulation studies**
 - **Whole blood, plasma, and serum storage for possible future research**
 - **Pharmacokinetics**
- **ECG**
- Adverse event recording and reporting

C 9.4.4 Day 7 Visit- ~~Remote~~ or In-person

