- Comparison between active and placebo treatment groups in proportion of all and \geq grade 3 adverse events as assessed by the National Institutes of Health, Division of AIDS Table for Grading the Severity of Adult and Pediatric Adverse Events (DAIDS AE Grading Table), corrected Version 2.1, July 2017.
- Incidence of AEs causing IP discontinuation
- Incidence of all-cause IP discontinuation or interruption
- Number of participants hospitalized due to adverse events regardless of cause

All adverse events will be listed by participant and will include:

- Event description
- Treatment group (active agent vs placebo)
- Clinician's assessment of severity and relationship to upamostat
- Outcome

The number and percentage of participants with AEs will be summarized for each treatment group. Overall treatment group differences may be compared using Chi-square tests or Fisher's exact tests.

Serious AEs, TEAEs, and hypersensitivity reactions will also be summarized. The counts and proportion of participants experiencing these events will be reported for each treatment arm. Treatment groups may be compared by Chi-square tests or Fisher's exact tests.

Permanent discontinuations or interruptions of upamostat due to AEs will be listed. The count and proportion of discontinuations of the study drug due to AEs will be reported.

Categorical safety measures including hospitalization will be summarized with counts and proportions of participants and may be compared by treatment using either a Chi-square test or a Fisher's exact test.

C 13.5.1.4 Exploratory

Prevalence and titer of anti-SARS-CoV-2 IgM and IgG antibodies at baseline and at Week 8 will be determined, and the effect of presence and titer of anti-SARS-CoV-2 IgG at baseline on treatment outcome will be assessed.

For participants receiving upamostat, targeted analysis of known host transmembrane protease polymorphisms will be described and compared to time to resolution of symptoms among key subgroups including by sex, race, and ethnicity.

C 13.5.1.5 Sub-Group Analyses

The primary analysis and each of the secondary analyses will be conducted in different patient subgroups of the mITT population for exploration of heterogeneity of treatment effect. The following patient subgroups will be analyzed:

- Age (< 30, 30-50, >50 years old)
- Sex
- Race
- Baseline symptom severity
- SARS-CoV-2 vaccination status
- Location (by continent)

C 13.6 Interim Analysis Plan

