2. CHANGES FROM THE PROTOCOL

Pharmacokinetic and exploratory objectives will not be analyzed as a part of this SAP. Available data may be included in final Study Data Tabulation Model (SDTM).

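### The host-protease polymorphism analysis is confined to upamostat recipients, so it cannot separate a genotype that alters drug efficacy (the stated objective) from one that alters the illness

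*Protocol*

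**What the plan says.** - **Objective.** Protocol C 4.1 lists as exploratory "To assess the impact of host transmembrane protease polymorphisms on drug efficacy". The synopsis (C 1.1) and SAP section 3.3 carry the same objective.
- **Analysis.** C 13.5.1.4 gives the only method: "For participants receiving upamostat, targeted analysis of known host transmembrane protease polymorphisms will be described and compared to time to resolution of symptoms". The comparison is to be broken down by demographic group (sex, race, ethnicity), not by treatment arm. The section mentions no placebo comparison, interaction term, model, test or significance level.
- **Heterogeneity.** C 13.5.1.5 plans analyses in "different patient subgroups of the mITT population for exploration of heterogeneity of treatment effect". Its list is age, sex, race, baseline symptom severity, vaccination status and location. Genotype is not on it.
- **Samples.** The Day 0 visit (C 9.4.2) includes "Polymorphisms of relevant host cellular proteases" for every enrolled participant, and the Schedule of Activities note reads "A sample of whole blood will be stored for planned future host protease polymorphism assessment". Neither is restricted by arm. Arm is unknown at sampling: "Both participants and study investigators will be blinded to this second randomization" (C 7.4.2).
- **SAP.** Section 2 states "Pharmacokinetic and exploratory objectives will not be analyzed as a part of this SAP", section 5.2.4 repeats the exclusion, and Appendix A gives its reason as the timing of data availability, decided before unblinding.

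**The concern.** Efficacy in this trial is the contrast between upamostat and placebo (C 13.4). An effect of genotype on efficacy is therefore a difference in that contrast between genotypes. Comparing genotypes among treated participants estimates something else: how genotype relates to recovery when everyone takes the drug.

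The protocol's own rationale makes the distinction matter. C 3.1 calls transmembrane serine proteases essential for fusion of the virus with the host cell, so a variant in one of them could plausibly change the course of the illness with or without the drug. If so, the treated-only comparison would show a genotype association even where the drug works equally well in all genotypes. Conversely, a prognostic effect in the opposite direction could cancel a real difference in drug effect.

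**Working it through.** **Identification.** Let h_P be the hazard ratio for recovery, carrier against non-carrier, on placebo, and let R be the treatment hazard ratio in carriers divided by that in non-carriers. Under proportional hazards:

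- genotype hazard ratio on placebo = h_P
- genotype hazard ratio on upamostat = h_P × R

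The objective concerns R. The treated arm supplies only the product. For example, h_P = 1.5 with R = 1 and h_P = 1 with R = 1.5 both give 1.5, while h_P = 0.667 with R = 1.5 gives 1.0. With both arms, R is the second line divided by the first.

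**The plan's own figures.** None is given for this analysis. As a check on the setup, the primary design was reproduced with exponential times, a 9-day control median, Day 28 censoring and 150 per arm (C 13.9). Spending 0.025 × 0.5² gives 0.00625 at the interim and 0.02178 at the final, as in C 13.6. Group-sequential power at a hazard ratio of 1.50 is 0.915 against 0.906 in Table 3, and at 1.42 it is 0.819 against 0.812.

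**Illustration.** Same setup, drug hazard ratio 1.5, 1,500 simulated trials per scenario, two-sided 5% tests. Carrier frequencies of 20%, 30% and 50% and the genotype effects are assumptions; the documents give none.

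| Truth | Active arm only: significant | Active arm only: median HR | Two-arm interaction: significant | Median ratio |
|---|---|---|---|---|
| Prognostic only, h_P 1.5, R 1 | 53-67% | 1.50-1.53 | about 6% | 0.99-1.01 |
| Modifier only, h_P 1, R 1.5 | 50-69% | 1.49-1.52 | 27-39% | 1.51-1.54 |
| Masked, h_P 0.667, R 1.5 | 4-6% | 1.00-1.01 | 25-39% | 1.48-1.51 |

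The first two rows look alike in the active arm. The third looks like no effect at all.

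**Closed-form check, active arm only.** SE(log HR) = 1/√(d·p·(1−p)), with d treated events and p the carrier frequency. Event probabilities by Day 28 on upamostat are 1 − exp(−1.5 × 28 × ln2/9) = 0.961 for non-carriers and 0.992 for carriers when h_P = 1.5.

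- 150 treated, p = 0.2: d = 145, SE = 0.208, z = 0.405/0.208 = 1.95, power 50%.
- 150 treated, p = 0.5: d = 146.5, SE = 0.165, z = 2.45, power 69%.
- 75 treated, p = 0.4: d = 73, SE = 0.239, z = 1.70, power 40%.

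These agree with the simulations to within about three percentage points.

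**Closed-form check, interaction with R = 1.5.** SE = √(1/(d₁p(1−p)) + 1/(d₀p(1−p))). Control event probability is 1 − exp(−28 × ln2/9) = 0.884.

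- 150 per arm, p = 0.2: d₁ = 145, d₀ = 132.6, SE = 0.300, power 27%, 95% interval around 1.5 of 0.83 to 2.70.
- 150 per arm, p = 0.5: d₁ = 146.5, d₀ = 132.6, SE = 0.240, power 39%, interval 0.94 to 2.40.
- 75 per arm, p = 0.4: d₁ = 73, d₀ = 66.3, SE = 0.346, power about 21%, interval 0.76 to 2.96.

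The documents do not state actual enrolment. The 75-per-arm case is an assumption that matches the planned interim point; SAP Appendix A says enrolment ended before that trigger was met.

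**The case against.** **No planned output is affected.** This stands. The SAP excludes the analysis, and nothing in the documents says that later work must follow the one sentence in C 13.5.1.4. That sentence is nevertheless the only method on record for samples the protocol intends to use, and the SAP dropped the analysis for timing, not because of the missing comparator.

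**The sentence promises description only.** This also stands in part. A reader might infer that the trial will report prognostic variants as affecting efficacy, at some known error rate. The documents do not support that: they set no test, level or reporting rule here. The most that can be said is that the result could be misread, because it is filed under an efficacy objective. The significance rates above depend on an assumed test, carrier frequency, genotype effect and sample size.

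**The wording may be loose.** The endpoint tables carry no arm restriction, and elsewhere the protocol describes entry into the product-specific arm, before the active/placebo step, as randomisation to upamostat. But receiving upamostat most naturally means taking active drug, and on either reading no treatment comparison is specified.

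**The remedy is weak too.** This is correct. With power of about 25-39% at N=300, and less in a smaller trial, the interaction model would miss most true modifiers of this size. That argues for presenting an estimate with its interval. It does not make the treated-only comparison an estimate of the right quantity.

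**Conclusion.** The point holds as a minor one. The mismatch between objective and method is plain from the text, and its consequence, that effect modification is not identifiable from one arm, needs no assumption about genotype frequency or sample size.

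Its practical size is conditional. For a prognostic hazard ratio of 1.5 with no effect modification, a two-sided 5% test in the active arm would be significant in about 40% of trials with 75 treated and 40% carriers, and in about 53-67% with 150 treated and 20-50% carriers. Neither the test nor these inputs come from the documents.

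The primary result, the secondary results and the SAP outputs are unaffected.

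**What to change.** Either of two changes resolves it, made in C 13.5.1.4 or in a separate plan for the stored samples.

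1. **Keep the objective.** Analyse both arms of the mITT population with a Cox model for time to sustained alleviation or resolution containing treatment, genotype and their interaction. Report the ratio of hazard ratios with its 95% interval, stated to be an estimate and not a confirmatory test. Cost: assaying placebo samples that the schedule already collects, and accepting wide intervals.
2. **Keep the analysis.** Reword the objective as a descriptive association between genotype and time to resolution among treated participants, with no claim about efficacy. Cost: the efficacy question goes unanswered, but no placebo assays are needed.

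Changing C 13.5.1.4 would be a protocol amendment. Since enrolment has ended and the SAP excludes this work, the separate plan is the more practical place, written before anyone links genotype to outcome.

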APPENDIX C ABBREVIATIONS

In addition to those listed in the Master Protocol

aPTT	Activated Partial Thromboplastin Time
CDER	Center for Drug Evaluation and Research
ECG	Electrocardiogram
INR	International Normalized Ratio
ITT	Intention to Treat
IxRS	Interactive Voice/Web Response System
MERS-CoV	Middle East respiratory syndrome-related coronavirus
mITT	Modified ITT
NGS	Next Generation Sequencing
PTT	Partial Thromboplastin Time
TMPRSS2	Transmembrane protease serine 2

APPENDIX C AMENDMENT HISTORY

Version	Date	Description of Change	Brief Rationale
V 1.0	25 Mar 2022	N/A	Initial Protocol
V 2.0	26 Apr 2023	
 1. Specified that this is a Phase 2 study. 2. Updated formatting and section numbering. 3. Updated study objectives and endpoints. 4. Updated study visits to clarify activities and procedures. 5. Added new information about the effectiveness of upamostat against current SARS-CoV-2 variants and pharmacologic parameters. 6. Updated hypotheses to look at sustained symptom alleviation or resolution. 7. Added clinical adverse event rates and percentages and new information for the 200 mg and 400 mg doses. 8. Removed the exclusion criteria for requires supplemental oxygen. Added exclusion criteria for patients with prolonged QT/QTc interval and/or increased susceptibility to arrhythmia with a list of defining criteria. 9. Added a new section with information regarding potential drug interactions and prohibited medications. 10. Specified that vaccination status will only be collected at baseline and Day 7 and that a 12 lead ECG will be performed. 11. Added Polymorphisms of relevant host cellular proteases to additional testing requirements. 12. Added specific screening assessments. 13. Added sample collection and testing information for PK evaluation. 14. Added and updated sections to outline pause and stopping criteria at the individual participant or 	
 1. Clarify study phase. 2. Consistency with Master Protocol. 3. Clarified for clear expectations. 4. Clarified for clear expectations. 5. Updated with current known information. 6. Consistency with Master Protocol. 7. Updated with new information. 8. Updated based off current information. 9. Updated with new information. 10. Clarified for clear expectations. 11. Clarified for clear expectations. 12. Clarified for clear expectations. 13. Clarified for clear expectations. 14. Added per FDA recommendation. 15. Updated with current information. 16. Clarified for clear expectations. 17. Consistency with Master Protocol. 18. Clarify concomitant medications with potential drug interactions.

Version	Date	Description of Change	Brief Rationale
		
Study/PSA level.
 
15. Updated the primary, secondary: virological, safety and tolerability, exploratory, and sub-group analysis outcome analysis information.
 
16. Updated interim analysis criteria and added information for the DSMB.
 
17. Added new section with sample size information.
 
18. Added a list of CYP3A4 Strong inhibitors and sensitive substrates for reference.
	
V 3.0	01 Jun 2023	
1. Pregnancy test added at D28 visit.
 
2. Race added as a sub-group for analysis.
	
1. Added per FDA recommendation.
 
2. Added per FDA recommendation.

V 4.0	01 Nov 2023	
1. Updated storage temperature range to be consistent with pharmacy manual.
 
2. Changed bullets to numbering.
 
3. Added clarification that overall symptom severity assessment question on the Daily Symptom Follow Up Questionnaire will be used for this endpoint.
 
4. Added upamostat dose to Description of Study Intervention
 
5. Added study staff may remind participant of Day 3 dose and venous blood draw according to PK regimen assignment.
 
6. Added reference to recently published upamostat pilot study.
 
7. Clarified corrected QT requirement and calculation. Moved from Master Protocol to PSA
 
8. Clarified "women of childbearing potential" definition.
 
9. Removed FSH requirement.
 
10. Removed one South Africa site. Added Uganda site
	
1. Updated for consistency.
 
2. Data monitoring request
 
3. DSMB recommendation
 
4. DSMB recommendation
 
5. Site feedback and recommendation
 
6. Updated information
 
7. Sites may apply different formulas or automated algorithms for recording the corrected QT interval. Clarified that same methodology for the calculation should be applied throughout the participant's study participation.
 
8. Clarification
 
9. Removed as most international sites not able to meet this testing requirement.
 
10. Updated site list

Version	Date	Description of Change	Brief Rationale
V 5.0	26 Jan 2024	
1. Updated order of activities2. Added caution for alcohol consumption while taking study drug3. Added Table of Contents	
1. Updated to clarify that screening activities under the PSA (ECG) cannot be performed until product specific informed consent and Step 1 randomization completed2. FDA request3. Added table

